1.2.7 Bavituximab: Overview

Bavituximab is a chimeric monoclonal antibody directed against the membrane phospholipid phosphatidylserine (PS). While phosphatidylserine is normally confined to the inner leaflet of the plasma membrane, phosphatidylserine is externalized during apoptosis, cell injury, cell activation and malignant transformation. Bavituximab exerts anti-tumor effects by targeting exposed phosphatidylserine in the tumor vascular endothelium which induces tumor vessel destruction and immune cell recruitment. Clinical studies have demonstrated that bavituximab is well-tolerated, and preliminary evidence suggests that bavituximab combined with immune checkpoint inhibitors has anti-tumor activity in HCC.

1.2.8 Bavituximab: Non-clinical experience

Phosphatidylserine is a highly immunosuppressive molecule typically expressed on the inner leaflet of the plasma membrane of normal cells but "flips" and becomes externalized to the outer leaflet of the plasma membrane on cells that line tumor blood vessels and tumor cells creating a specific target for anticancer treatments. Bavituximab is an engineered immunoglobulin gamma 1 (IgG1) chimeric (human/mouse) mAb containing the variable region sequences of the murine phosphatidylserine targeting mouse antibody 3G4(2aG4) and human IgG1 k constant region sequences that targets phosphatidylserine (PS) after binding to 2-glycoprotein 1 (2GP1). By targeting phosphatidylserine, bavituximab induces tumor-infiltrating lymphocytes and pro-inflammatory cytokines which is enhanced with anti-PD-1/PD-L1 therapy. In addition, bavituximab repolarizes myeloid derived suppressor cells and M2 macrophages to M1, resulting in dendritic cell maturation and induction of tumor-specific cytotoxic T-lymphocyte immunity.

Nonclinical experiments have shown that antibody-mediated phosphatidylserine targeting can override phosphatidylserine-mediated immunosuppression, reactivate innate tumor immunity, and evoke adaptive antitumor immunity. In genetically modified nonclinical murine tumor models, phosphatidylserine targeting induces potent tumor-specific T-cell immunity in the transgenic adenocarcinoma mouse prostate tumor model such that the combination of anti-PS with castration cured 35% of the animals, compared to none in control groups. In separate pre-clinical studies, the use of antibodies against PD-1 or PD-L1 have demonstrated

similar activity as single agents and when combined with other immune oncology agents.

To support clinical development, bavituximab was evaluated in a series of dose range finding, repeated dose and specialized IV toxicology studies in appropriate species and in vitro systems. In vivo toxicology studies consisted of non-GLP dose range finding studies in the Sprague-Dawley® (SD) rat, rabbit and cynomolgus monkey as single IV dose administration, followed by GLP 8-week once-weekly dosing toxicology studies in the rat and monkey. The reversibility of any observed toxicity was determined in recovery studies included as part of the protocol for selected studies. The in vivo studies employed intravenous bolus dosing of bavituximab according to the current clinical dosing regimen and route of administration. Toxicokinetic (TK) analyses were conducted in rats and monkeys to facilitate correlating observed toxicity to systemic exposure to bavituximab.

The nonclinical safety assessment program that has been undertaken fully supports the continual use of bavituximab in clinical trials in oncology patients. The nonclinical effects of bavituximab have been assessed in a comprehensive panel of studies, addressing the relationships of pharmacology, pharmacokinetics/toxicokinetics, immunogenicity and toxicology; the target tissues for toxicity; the NOAELs and LOAELs; the noninvasive monitors for the key toxicologic responses; and the reversibility of adverse effects. Among the recovery animals at the high dose (100 mg/kg) in the rat toxicology study, there remained evidence of microscopic sub endocardial inflammation and/or fibrosis, however, there were no coagulation abnormalities. Similarly, bavituximab-related microscopic changes in monkeys were confined to a mild thrombus within the right ventricle of one male at 100 mg/kg and no coagulation abnormalities in the recovery phase. Results from the bavituximab nonclinical program to date indicate a therapeutic benefit of combining bavituximab with conventional (chemotherapy) or immunotherapy (checkpoint blockade) for continued clinical evaluations and support the safety of the proposed dose of 3 mg/kg bavituximab administered intravenously once weekly in patients.

1.2.9 Bavituximab: Clinical experience

To date, the clinical development program of bavituximab has enrolled approximately 900 patients, of whom over 600 patients have been treated with bavituximab. Most patients were treated with combination therapy in oncology studies. Common AEs (20%) were reported in patients receiving bavituximab, including the following: nausea, alopecia, fatigue, diarrhea, neutropenia, anemia, pyrexia, and asthenia. Many of the reported common AEs were considered to be related to the concomitant administration of chemotherapy or the patient's underlying malignancy.

Phase I and Ib single-agent studies of bavituximab in combination with chemotherapy have been completed in patients with advanced cancer. Based on efficacy results from these studies and on PK data (which determined the maximum binding of β 2-GP1), a dose of 3 mg/kg bavituximab was determined and selected for further clinical study. The studies also showed the tolerability profile to be consistent with expectations based on animal studies and demonstrated adequate efficacy to warrant further study. Several Phase II studies of bavituximab in combination with chemotherapy have been completed.

The double-blind, placebo-controlled, multicenter, phase 3 SUNRISE study tested the efficacy and safety of bavituximab combined with docetaxel in patients with previously treated advanced non-squamous lung adenocarcinoma.²⁶ Patients were randomized 1:1 to receive docetaxel 75 mg/m² intravenously on day 1 of a

21-day cycle plus blinded study treatment (either placebo or bavituximab 3 mg/kg intravenously weekly). The primary end point was overall survival and secondary end points included progression-free survival, objective response rate, and safety. 597 patients were enrolled and the median overall survival was 10.5 months in the docetaxel plus bavituximab arm and 10.9 months in the docetaxel plus placebo arm. There was also no difference in progression-free survival (HR 1.00; 95% CI 0.82–1.22; P = 0.990) or objective response rates (14% in the docetaxel plus bavituximab arm and 11% in the docetaxel plus placebo arm; P = 0.18). In a post hoc analysis, overall survival favored the bavituximab arm among patients who received immune checkpoint inhibitor therapy after study therapy (n = 93, 16%) with a median survival time not reached versus 12.6 months (HR 0.46; 95% CI 0.26–0.81; P = 0.006). There was no apparent difference in rates of characteristic immune-related adverse events, and AEs in both arms were largely consistent with AEs expected with docetaxel monotherapy. While this study did not support the addition of bavituximab to chemotherapy in refractory lung adenocarcinoma, the improved overall survival of patients who received bavituximab and subsequent immunotherapy rather than targeted therapies or chemotherapy suggests that bavituximab may sensitize cancers to immune checkpoint inhibitors.

Bavituximab plus sorafenib was examined in a single-arm phase 2 trial of patients with unresectable HCC, Eastern Cooperative Oncology Group (ECOG) score \leq 2, and Child-Pugh score A/B7.²⁷ Time to progression was the primary endpoint and 38 patients received intravenous bavituximab 3 mg/kg weekly and oral sorafenib 400 mg twice daily. The median time to progression of patients receiving bavituximab and sorafenib was 6.7 months, which did not reach pre-specified significance. Treatment-related AEs were observed in 63% of patients, with the most commonly reported therapy-related symptoms being diarrhea (32%), fatigue (26%), and anorexia (24%). There were no grade 4-5 AEs and grade 3 AEs included diarrhea (5%), vomiting (3%), upper gastrointestinal bleeding (3%), fatigue (3%), hypertension (3%), and palmar-plantar erythrodysesthesia syndrome (3%). These AEs were consistent with toxicities expected with monotherapy sorafenib. While this study did not provide evidence for improved efficacy of bavituximab plus sorafenib over sorafenib alone, the combination regimen was well-tolerated and safe in patients with advanced HCC and underlying liver disease.²⁷

Bavituximab in combination with the anti-PD-1 antibody pembrolizumab is now under investigation across 3 disease types including gastroesophageal cancers (NCT04099641), head and neck cancers (NCT04150900), and HCC (NCT03519997). A single-arm phase 2 study with a two-stage design for patients with unresectable HCC is currently being conducted at the Harold C. Simmons Comprehensive Cancer Center and Parkland Hospital and Health System. Patients receive pembrolizumab 200 mg intravenously every 3 weeks and bavituximab 3 mg/kg intravenously weekly. The primary endpoint is the best objective response rate. This study is currently enrolling in its second stage after meeting its predefined response rate to continue enrollment. Preliminary analysis of 36 patients who received at least one infusion of pembrolizumab and bavituximab and evaluable for safety shows that this combination is safe and well tolerated in patients with advanced HCC with no unexpected safety events. Treatment-related AEs are shown below:

Treatment-related adverse event	All grade (%)	Grade 3 or 4 (%)
Colitis/diarrhea	7 (19.4)	2 (5.6)
Aspartate aminotransferase increased	5 (13.9)	0
Alanine aminotransferase increased	4 (11.1)	0

Maculopapular rash	4 (11.1)	1 (2.8)
Chills	3 (8.3)	0
Pruritus	3 (8.3)	0
Arthralgia	2 (5.6)	0
Fatigue	2 (5.6)	0
Thrombocytopenia	2 (5.6)	0
Abdominal pain	1 (2.8)	0
Creatinine increased	1 (2.8)	0
Dyspnea	1 (2.8)	0
Fever	1 (2.8)	0
Mucositis	1 (2.8)	0
Albumin decreased	1 (2.8)	0

1.3 Rationale

Sensitizing HCC to immunotherapy using axitinib. Preclinical evidence indicates that VEGF and VEGF-dependent angiogenesis may induce immune suppression in tumors by impairing antigen presenting cells and effector T-cells, and enhancing T-regulatory cells and monocytes.²⁸ Disruption of the endothelium may also enhance lymphocyte recruitment within tumors.^{29,30} Thus, targeting VEGF may reprogram the tumor immune microenvironment to render cancers more vulnerable to immunotherapies. Indeed, the use of anti-VEGF strategies as an immunotherapy adjuvant has been associated with clinical benefit in multiple cancer types including HCC, and no new safety signals.^{8,31-33} While the clinical benefit of monotherapy axitinib in HCC is modest, use of axitinib as an immunotherapy adjuvant may circumvent primary resistance mechanisms to immune checkpoint inhibitors in HCC leading to more frequent or robust anti-tumor immunity. This is consistent with results from the phase 3 IMbrave150 study which demonstrated the superiority of atezolizumab plus bevacizumab versus sorafenib alone.⁸

Rationale for combining axitinib and immune checkpoint inhibitor with the anti-phosphatidylserine antibody bavituximab. Phosphatidylserine is a cytoplasmic-facing anionic phospholipid which has multiple essential functions in cellular membranes.^{34,35} Externalization of phosphatidylserine occurs as a result of apoptosis or cellular stress, but is also frequently observed in cancer cells and within stromal cells.³⁴ Of therapeutic relevance, exposed phosphatidylserine and phosphatidylserine-dependent receptors including the Tyro3, Axl, and Mer (TAM) family of negative immune regulators facilitate cancer immune escape.³⁴ Indeed, preclinical evidence indicates that antibody-based targeting of phosphatidylserine promotes pro-inflammatory pathways, recruitment of tumoricidal macrophages, dendritic cell maturation, and potent T-cell immunity in multiple cancer models.³⁶ While bavituximab has been demonstrated to be well tolerated as a single agent and in combination with chemotherapy, its use as a single agent in a phase I study of refractory advanced solid cancers and in combination with docetaxel in advanced non-small-cell lung cancer did not show significant clinical benefit.^{26,37,38} Notably, prior use of bavituximab was not guided by its immunogenic mechanism of action. The pleiotropic pro-inflammatory and -immunogenic effects of bavituximab on tumor cells, immune cells, and stroma suggests that it may enhance the activity of immune checkpoint inhibitors. This is supported by preclinical evidence that targeting phosphatidylserine enhances either PD-1 or CTLA-4 blockade in melanoma, breast, and colon cancer models, and preliminary results from a phase II study underway at UT Southwestern testing the combination of bavituximab and pembrolizumab in HCC.³⁹⁻⁴¹ Initial results from a two-stage phase II study testing bavituximab plus pembrolizumab in advanced HCC has demonstrated good tolerability and promising activity based on objective response rates meeting pre-specified goals in order to transition to the second stage of the study. Given the complimentary

immune augmenting mechanisms of targeting VEGF and phosphatidylserine, we hypothesize that combination axitinib, bavituximab, and avelumab, a PD-L1 antibody, represents a novel and rational immunotherapy regimen in HCC. We propose to test this by studying the clinical efficacy and safety of combination axitinib, bavituximab, and avelumab treatment in a single arm phase II trial using a two-stage design.

1.4 Rationale for Treatment Beyond Progression

Across cancer types, immune checkpoint inhibitors have been shown to induce complete response, partial response, and stable disease after initial evidence of radiographic increase in tumor burden. This initial increase in tumor burden may be attributed to immune-cell infiltration in the setting of a T-cell response. Therefore, this study will allow all patients to continue their assigned treatment after apparent radiographic progression per RECIST v1.1, provided the benefit-risk ratio is judged to be favorable by the investigator. Treatment beyond progression should be considered when the patient is stable (or improving) symptomatically and if tumor reassessment can be performed within a short period.

1.5 Correlative Studies

Molecular profiling including exome and transcriptome sequencing of baseline or multiplex immunohistochemistry of archived tissue specimens will allow us to identify predictive markers of treatment response. As this testing will be performed on tissue obtained as a component of routine care, there is no additional risk to the patient. Tissue sampling at the time of progression is encouraged but not required. Tissue at progression may undergo similar testing to identify markers or mechanisms of resistance.

Archival tissue will also be examined using the Xerna™ TME Panel which is a RNA-based gene expression assay to classify patients based on the biology of the tumor microenvironment (TME).

2.0 STUDY OBJECTIVES

2.1 Primary Objectives

2.1.1 To determine the best objective response rate assessed by RECIST guidelines (version 1.1) of combination axitinib, bavituximab, and avelumab in patients with advanced HCC not previously treated with systemic therapies.

2.2 Secondary Objectives

2.2.1 To determine the disease control rate, overall survival, 6-month progression-free survival, and duration of response of combination axitinib, bavituximab, and avelumab compared to historical controls.

2.2.2 To evaluate the overall safety profile of combination axitinib, bavituximab, and avelumab.

2.3 Exploratory Objectives

2.3.1 To explore the objective response rate as assessed by iRECIST of combination axitinib, bavituximab, and avelumab in patients with advanced HCC.

- 2.3.2 To explore the utility of tissue and/or serum-based markers as predictors of therapy response.

2.4 Endpoints

Primary endpoint:

Objective response rate (ORR) based on Investigator assessment per RECIST v.1.1.

Secondary endpoint:

Progression-free survival (PFS), overall survival (OS), and duration of response (DR) based on Investigator assessment, per RECIST v.1.1.

Adverse events (AEs) and laboratory abnormalities as graded by National Cancer Institute (NCI) Common Terminology Criteria for Adverse Events (CTCAE) v5.0.

3.0 SUBJECT ELIGIBILITY

Eligibility waivers are not permitted. Subjects must meet all of the inclusion and exclusion criteria to be registered to the study. Study treatment may not begin until a subject is registered.

3.1 Inclusion Criteria

- 3.1.1 Patient must have a histologically confirmed diagnosis consistent with HCC; known fibrolamellar HCC, or combined HCC-cholangiocarcinoma will be excluded.
- 3.1.2 Locally advanced or metastatic disease
- 3.1.2.1 Patients with locally advanced or metastatic disease must have disease deemed not amenable to surgical and/or locoregional therapies or patients who have progressed following surgical and/or locoregional therapies.
- 3.1.2.2 Measurable disease, as defined as lesions that can accurately be measured in at least one dimension according to RECIST version 1.1 at least 1 cm with contrast enhanced dynamic imaging (magnetic resonance imaging or computed tomography).
- 3.1.3 Availability of recent formalin-fixed, paraffin-embedded (FFPE) tumor tissue block or slides (biopsied tumor lesion should not be a RECIST target lesion): 1) the biopsy or resection was performed within 2 years of AND 2) the patient has not received any intervening systemic anti-cancer treatment from the time the tissue was obtained.
- 3.1.4 Prior therapy is allowed provided the following are met: at least 4 weeks since prior locoregional therapy including surgical resection, chemoembolization, definitive radiotherapy with intent of disease control, or ablation. Provided target lesion has increased in size by 25% or more or the target lesion was not treated with locoregional therapy. Patients treated with palliative radiotherapy for symptoms will be eligible as long as the target lesion is not the treated lesion and radiotherapy will be completed at least 2 weeks prior to study drug administration.
- 3.1.5 Age \geq 18 years
- 3.1.6 Child-Pugh Score A
- 3.1.7 ECOG Performance score of 0-1

- 3.1.8 Adequate organ and marrow function as defined below:
- 3.1.8.1 Platelet count $\geq 50,000/\text{mm}^3$
 - 3.1.8.2 Hgb ≥ 8.5 g/dl
 - 3.1.8.3 Absolute neutrophil $\geq 1,500$ cells/ mm^3
 - 3.1.8.4 Total bilirubin ≤ 2.0 mg/ml
 - 3.1.8.5 INR ≤ 1.7
 - 3.1.8.6 AST, ALT ≤ 5 times ULN
 - 3.1.8.7 Serum creatinine ≤ 1.5 mg/dL or creatinine clearance ≥ 50 mL/min
 - 3.1.8.8 Albumin ≥ 2.5 g/dl
- 3.1.9 All men, as well as women of child-bearing potential must agree to use adequate contraception (hormonal or barrier method of birth control; abstinence) 4 weeks prior to study entry, for the duration of study participation, and for 90 days following completion of therapy. Should a woman become pregnant or suspect she is pregnant while participating in this study, she should inform her treating physician immediately.
- 3.1.9.1 A female of child-bearing potential is any woman (regardless of sexual orientation, marital status, having undergone a tubal ligation, or remaining celibate by choice) who meets the following criteria:
- Has not undergone a hysterectomy or bilateral oophorectomy; or
 - Has not been naturally postmenopausal for at least 12 consecutive months (i.e., has had menses at any time in the preceding 12 consecutive months).
- 3.1.10 Women of childbearing potential must have a negative serum pregnancy test within 72 hours prior to receiving the first dose of study medication.
- 3.1.11 Subjects are eligible to enroll if they have non-viral-HCC, or if they have HBV-HCC, or HCV-HCC defined as follows:
- 1) HBV-HCC: Controlled (treated) hepatitis B subjects will be allowed if they meet the following criteria: Antiviral therapy for HBV must be given for at least 12 weeks and HBV viral load must be less than 100 IU/mL prior to first dose of study drug. Subjects on active HBV therapy with viral loads under 100 IU/ml should stay on the same therapy throughout study treatment. Subjects who are anti-HBc (+), negative for HBsAg, negative for anti-HBs, and have an HBV viral load under 100 IU/mL do not require HBV anti-viral prophylaxis.
 - 2) HCV-HCC: Active or resolved HCV infection as evidenced by detectable HCV RNA or antibody. Patients who have failed HCV therapy as evidenced by detectable HCV RNA will be eligible. Subjects with chronic infection by HCV who are treated (successfully or treatment failure) or untreated are allowed on study. In addition, subjects with successful HCV treatment are allowed as long as there are ≥ 4 weeks between completion of HCV therapy and start of study drug. Successful HCV treatment definition: SVR12.

- 3.1.12 Ability to understand and the willingness to sign a written informed consent.
- 3.1.13 Patients who have received the vector, protein subunit, or nucleic acid COVID-19 vaccines are eligible to enroll.

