6.1.1 Definitions

Evaluable for toxicity. All subjects will be evaluable for toxicity from the time of their first treatment with study therapy.

Evaluable for objective response. Only those subjects who have measurable disease present at baseline, have received at least one cycle of therapy, and have had their disease re-evaluated will be considered evaluable for response. These subjects will have their response classified according to the definitions stated below. (Note: Subjects who exhibit objective disease progression prior to the end of cycle 1 will also be considered evaluable.)

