All other lesions are considered non-measurable, including small lesions (longest diameter < 10 mm or pathological lymph nodes with ≥ 10 to < 15 mm short axis) as well as truly non-measurable lesions. Lesions considered truly non-measurable include: leptomeningeal disease, ascites, pleural or pericardial effusion, inflammatory breast disease, lymphangitic involvement of skin or lung, abdominal masses/abdominal organomegaly identified by physical exam that is not measurable by reproducible imaging techniques.

Target lesions.

All measurable lesions up to a maximum of five lesions total (and a maximum of two lesions per organ) representative of all involved organs should be identified as target lesions.

Non-target lesions. All other lesions (or sites of disease) including any measurable lesions over and above the five target lesions should be identified as **non-target lesions** and should also be recorded at baseline. Measurements of these lesions are not required, but the presence or absence of each should be noted throughout follow-up.

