6.1.4.3 Evaluation of Best Objective Response

The best objective response is the best response recorded from the start of the treatment until disease progression/recurrence (taking as reference for progressive disease the smallest measurements recorded since the treatment started). The subject’s best response assignment will depend on the achievement of both measurement and confirmation criteria.

Time point response: patients with target (+/- non-target) disease.			
Target lesions	Non-target lesions	New lesions	Objective response
CR	CR	No	CR
CR	Non-CR/non-PD	No	PR
CR	Not evaluated	No	PR
PR	Non-PD or not all evaluated	No	PR
SD	Non-PD or not all evaluated	No	SD
Not all evaluated	Non-PD	No	NE
PD	Any	Yes or No	PD
Any	PD	Yes or No	PD
Any	Any	Yes	PD

CR = complete response, NE = not evaluable, PD = progressive disease, PR = partial response, SD = stable disease.

Time point response: patients with non-target disease only.		
Non-target lesions	New lesions	Objective response
CR	No	CR
Non-CR/non-PD	No	Non-CR/non-PD
Not all evaluated	No	NE
Unequivocal PD	Yes or No	PD
Any	Yes	PD

CR = complete response, NE = not evaluable, PD = progressive disease

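### Sections 3.1.3 and 6.1.2 disagree on whether a biopsied lesion can be a target lesion, so a patient whose only measurable lesion was biopsied may be counted in the ORR with no route to a partial response

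*Combined protocol and SAP*

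**What the plan says.** Four parts of the protocol bear on this.

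- **Tissue.** Section 3.1.1 requires histology: "Patient must have a histologically confirmed diagnosis consistent with HCC". Section 3.1.3 requires tumor tissue from a biopsy or a resection within a two-year window, and adds that the "biopsied tumor lesion should not be a RECIST target lesion".
- **Target selection.** Section 6.1.2 says that measurable lesions, to a limit of five in total and two in any organ, "representative of all involved organs should be identified as target lesions". It makes no exception for a biopsied lesion.
- **Entry and evaluability.** Section 3.1.2.2 asks for "Measurable disease, as defined as lesions that can accurately be measured in at least one dimension according to RECIST version 1.1". Section 6.1.1 defines the response-evaluable set as "Only those subjects who have measurable disease present at baseline, have received at least one cycle of therapy, and have had their disease re-evaluated". Neither asks for a measurable lesion that is allowed to be a target.
- **Response.** Section 6.1.4.1 defines PR on the target-lesion sum only. The second table in 6.1.4.3, headed "Time point response: patients with non-target disease only", has outcomes CR, non-CR/non-PD, NE and PD, and no PR.

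Section 10.2 counts CR or PR as response. It continues to stage 2 on 2 or more responses in 14 and rejects the 14% null on 7 or more in 29.

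**The concern.** For a biopsied measurable lesion, 3.1.3 and 6.1.2 cannot both be followed. The choice matters most when that lesion is the only measurable one. Under 3.1.3 the patient has no target lesion and is scored on the table without a PR row. Under 6.1.2 the lesion is a target and a 30% shrinkage is a PR. The same scans then give two different values of the primary endpoint.

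ORR is investigator-assessed (2.4) and the Study Summary lists two centers, so the point could be settled differently from one patient to the next. If 3.1.3 is followed without any limit on entry, such patients sit in the denominators of the 2/14 and 7/29 rules almost as built-in non-responders. The cost would be lost power and a higher chance of stopping an active regimen at stage 1.

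**Working it through.** **Step 1: one patient, two rules.** Take a patient with a single measurable lesion, biopsied before entry.

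| Question | 3.1.3 followed | 6.1.2 followed |
|---|---|---|
| Measurable disease at baseline? | Yes | Yes |
| Lesion is a target? | No | Yes |
| Table in 6.1.4.3 | Non-target disease only | Target disease |
| PR possible? | No | Yes |
| CR possible? | Yes, but 6.1.4.2 requires all non-target lesions to disappear and the tumor marker to normalize | Yes |

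The replacement rule in 10.1 and 10.2 covers CR, PR or SD without confirmatory imaging. It does not name non-CR/non-PD, so the handling of a patient with that outcome is also unstated.

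**Step 2: reproduce the design.** Inputs from 10.2: null rate 0.14, alternative 0.34, 14 + 15 = 29 patients, continue on 2 or more, reject on 7 or more. With X1 ~ Bin(14, p) and X2 ~ Bin(15, p),

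P(reject) = Σ (x = 2 to 14) P(X1 = x) · P(X2 ≥ 7 − x).

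This gives 0.0973 at p = 0.14 and 0.9002 at p = 0.34. The stated 0.10 and 0.9 are reproduced. Power is only just above 0.90, so there is no slack.

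**Step 3: effect if 3.1.3 is followed and entry is not restricted.** Let f be the share of evaluable patients whose only measurable lesion was biopsied. The documents do not give f, so it is varied. Assume no CRs among these patients and the design rate in all others. The effective rate is then 0.34 × (1 − f) under the alternative and 0.14 × (1 − f) under the null. The stage 1 false stop is P(X1 ≤ 1) at the effective alternative rate.

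| f (assumed) | Effective rate, alternative | Power | Stage 1 false stop | Effective rate, null | Type I error |
|---|---|---|---|---|---|
| 0 | 0.340 | 0.900 | 0.024 | 0.140 | 0.097 |
| 5% | 0.323 | 0.864 | 0.033 | 0.133 | 0.078 |
| 10% | 0.306 | 0.818 | 0.043 | 0.126 | 0.062 |
| 20% | 0.272 | 0.698 | 0.073 | 0.112 | 0.036 |

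**Step 4: sensitivity.** If these patients had an assumed 3% CR rate, the effective alternative rate is 0.34 × (1 − f) + 0.03 × f. Power is then 0.867, 0.827 and 0.722 at f = 5%, 10% and 20%. For small shares with no CRs, f = 1/29 gives a rate of 0.328 and power 0.876, and f = 2/29 gives 0.317 and 0.848.

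**The case against.** The strongest reply is that the loss needs one particular combination of readings: 3.1.3 must override 6.1.2 on target selection and yet not restrict entry. Several points support that reply.

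- A reader might infer that such a patient can never have a PR. The documents do not support that. Under 6.1.2 the lesion is a target, and 3.1.3 says only that it should not be one, which leaves the investigator some room. Even under 3.1.3, CR remains a route to response.
- The patient may not be eligible at all. The restriction sits inside an inclusion criterion, and section 3.0 requires all criteria to be met. Read with 3.1.2.2, it could mean that another measurable lesion is needed, and then no bias arises. The text does not say so, however. Section 3.1.4 ties eligibility to the target lesion for locoregional therapy and palliative radiotherapy, but no equivalent sentence exists for biopsy.
- Universal histology does not mean that every patient carries a biopsied lesion. Resection tissue is accepted, which lowers f.
- In patients with several lesions, leaving a biopsied lesion out of the target sum is not a defect in itself. The caps of five and two already leave some measurable lesions as non-target.
- The restriction may have a measurement reason. Tissue may be up to two years old, but sections 1.5 and 9.0 also mention baseline tissue, so a biopsy can fall close to the baseline scan.

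All of these stand as limits on reach and size. None of them says which of 3.1.3 and 6.1.2 governs.

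**Conclusion.** The contradiction is real and touches the primary endpoint: two stated rules classify the same lesion, and so possibly the same patient, differently. That much rests on the text alone.

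The size is conditional. It requires that 3.1.3 is followed, that such patients are enrolled, that CRs among them are absent or rare, and that f is above zero. Under those assumptions power is 0.86, 0.82 or 0.70 at f = 5%, 10% or 20%. Nothing in the documents indicates which value of f is realistic, or that it is as high as 20%.

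A reader might conclude that the stated power of 0.90 is not delivered. That does not follow, because the design figures are correct as calculated and the shortfall depends on an unknown f and on a contested reading. Nor does the problem favor the regimen: type I error falls from 0.097 to 0.062 at f = 10%. The risk is of missing activity, not of claiming it falsely.

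**What to change.** Reconcile 3.1.3, 3.1.2.2, 6.1.1 and 6.1.2 so that every evaluable patient has a target lesion. Either of two clauses would do.

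1. State in 3.1.3 and 6.1.2 that a biopsied lesion may be a target when it is the only measurable lesion and the baseline scan was done after the biopsy. The clause should also say how a sole lesion biopsied after that scan is handled; otherwise the gap stays open for that patient. The cost is some post-biopsy noise in the measurement.
2. Keep the restriction, write it into 6.1.2 as an exception, and state in 3.1.2.2 that at least one non-biopsied measurable lesion is required. The cost is a few patients turned away.

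Under either option, 6.1.1 should refer to a target lesion at baseline and not only to measurable disease. With f = 0 the calculated power is 0.900 again, and the sample size and decision rules need no change.
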